### 6.3. Exploratory Efficacy Endpoints

The exploratory efficacy endpoints are defined in [Section 1.1.3](#).

Continuous endpoints will be summarized using descriptive statistics. A p-value will be computed for between treatment comparisons using a van Elteren (vE) test (van Elteren 1960). The Wilcoxon–Mann–Whitney (WMW) test (Mann and Whitney 1947; Wilcoxon 1945) is widely used nonparametric approach to compare two treatments. In the

presence of stratum factors such as gestational age or ItchRO(Obs) Score, the van Elteren test, a stratified WMW test, can be used to adjust for the stratification factors. It was shown by Qu et al. (2008) that vE test preserves the type I error rate regardless of the existence of the stratum effects, and is better than the WMW test when the stratum effects are large.

A non-strata adjusted 95% CI for the difference in means between treatment groups will also be presented. A test of equality of variances will be performed. If the null hypothesis that the variances are equal is rejected, then the 95% CI will be constructed using a Satterthwaite approximation. Otherwise, the variances will be pooled.

For categorical endpoints, the number and percent for each category will be displayed. For responder-type analyses, within a treatment group, an approximate 95% CI will be presented using a stratified Wilson confidence interval (Yan and Su 2010). A 95% CI comparing two treatment groups based on stratum-adjusted MH proportions as described in Section 6.2 will also be generated. A stratified CMH test will be used to calculate the p-value for the difference between treatment groups. The method is applicable to the following endpoints:

- Proportion of participants with an early term delivery (37–38 weeks 6 days, inclusive)
- Proportion of participants with a full-term delivery ( $\geq 39$  weeks)
- Proportion of participants experiencing a perinatal death
- Proportion of participants with a spontaneous preterm delivery
- Proportion of participants with an iatrogenic preterm delivery attributable to ICP
- Proportion of neonates requiring neonatal intensive care unit (NICU) admission for  $\geq 12$  hours between birth and hospital discharge
- Proportion of neonates with meconium-stained amniotic fluid at delivery
- Proportion of participants requiring rescue medication for ICP
- Proportion of neonates with Apgar score  $< 7$  at 5 minutes of life
- Proportion of neonates with umbilical cord pH  $< 7.0$  at birth

“Responder” analyses for composite perinatal outcomes will be performed using baseline sBA and ItchRO and the change at Week 3 values in sBA and ItchRO as covariates and, separately, using the Week 3 values themselves (instead of the change at Week 3).

The change in total sBA from Week 3 (primary endpoint) to delivery will be considered, and the difference between treatment groups will be tested using a randomization-based version of rank analysis of covariance (ANCOVA) (Stokes et al. 2012). In a similar manner, the change from baseline in total sBA concentration to the time of delivery will also be explored. An additional analysis will be performed that examines the change from baseline to delivery but that averages across the last two time points on or prior to delivery. Similar analyses will be performed for Adult ItchRO. Associations between the changes from baseline to Week 3 in total sBA and Adult ItchRO will be assessed using Pearson’s and Spearman’s correlation coefficient. Additionally, a scatterplot of two variables will also be produced.

The following endpoints will be summarized by treatment arm and the summary statistics by treatment arm and the treatment differences will be tabulated:

- Mean gestational age at delivery
- Mean birth weight percentile
- Mean placental weight percentile
- Means for umbilical cord blood sBA, total cholesterol, LDL cholesterol, and glucose
- Mean maternal estimated blood loss at delivery
- Mean time from randomization to delivery

Further exploratory efficacy endpoints include continuous and binary endpoints on additional perinatal outcomes. The analysis of continuous endpoints will follow the same approach as other exploratory efficacy endpoints. Binary outcomes will be analyzed in the same manner as the secondary efficacy endpoint for composite perinatal outcomes.

The secondary endpoint of composite perinatal outcomes will also be explored using an ordinal scale, with ranks assigned according to the severity of the outcomes specified within [Section 3.2](#).

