#### 10.4.1.4. Exploratory Efficacy Endpoints

The exploratory efficacy endpoints are defined in [Section 3.4](#). The change in total sBA from Week 3 (primary endpoint) to delivery will be considered, and the difference between treatment groups will be tested using a randomization-based version of rank analysis of covariance (ANCOVA; [Stokes et al. 2012](#)). In a similar manner, the change from baseline in total sBA concentration to the time of delivery will also be explored. An additional analysis will be performed that examines the change from baseline to delivery but that averages across the last 2 time points on or prior to delivery. Similar analyses will be performed for Adult ItchRO. Associations between the changes from baseline to Week 3 in total sBA and Adult ItchRO will be assessed using either Pearson’s or Spearman’s correlation coefficient. “Responder” analyses for composite perinatal outcomes will be performed using baseline sBA and ItchRO and the change at Week 3 values in sBA and ItchRO as covariates and, separately, using the Week 3 values themselves (instead of the change at Week 3).

Change in biomarkers of bile acid synthesis, inflammation, and pruritogens as well as the proportion of participants with sBA <40 µmol/L at the end of the treatment period will also be explored. The change in biomarkers will follow the same approach as other exploratory efficacy endpoints described above. The proportion of participants with sBA <40 µmol/L at the end of the treatment period will be analyzed in the same manner as the secondary efficacy endpoint for composite perinatal outcomes.

Further exploratory efficacy endpoints include continuous and binary endpoints on additional perinatal outcomes. The analysis of continuous endpoints will follow the same approach as other exploratory efficacy endpoints described above. Binary outcomes will be analyzed in the same manner as the secondary efficacy endpoint for composite perinatal outcomes. Additional details will be included within the SAP.

The secondary endpoint of composite perinatal outcomes will also be explored using an ordinal scale, with ranks assigned according to the severity of the outcomes specified within [Section 3.2](#).

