### **10.4.3. Other Analyses**

#### **10.4.3.1. Patient-Reported Outcomes**

The effect of volixibat on additional measures of pruritus efficacy and quality of life in adult participants with ICP will be evaluated via the following endpoints:

- Change from baseline in the 5-D Itch Scale
- Change from baseline in CSS
- Change from baseline in EQ-5D-5L
- Change from baseline in PROMIS SF Fatigue 7a
- Change from baseline in PROMIS SF Sleep Disturbance
- Change from baseline in PIS-Itch

Because the PROs are administered only at baseline, Week 3, and end of treatment, the change from baseline will be compared between the 2 groups with use of rank ANCOVA with adjustment for baseline with the Mann-Whitney odds as the estimand. The estimates and CIs can be calculated using the R package sanon ([Kawaguchi and Koch 2015](#)).

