### 3.3. Strata and Covariates

Participants will be randomly assigned to treatment groups via the interactive voice or web response system (IXRS).

- For the primary cohort, a dynamic allocation method, introduced by Pocock and Simon (1975) will be adopted to balance participant assignment between treatment arms based on the following factors: gestational age (<32 weeks or ≥32 weeks) at randomization, presence/absence of gestational diabetes, and highest sBA before randomization (<40 µmol/L, ≥40 µmol/L to <100 µmol/L, or ≥100 µmol/L) after confirmation of study eligibility. Participants with highest pre-randomization sBA <40 µmol/L shall comprise no more than 33% of the primary cohort for Part 1 and Part 2, respectively.
  - For Part 1, in a 1:1:1 ratio via a computer-generated randomization schedule to receive volixibat 20 mg BID, volixibat 80 mg BID, or placebo BID
  - For Part 2, in a 1:1 ratio via a computer-generated randomization schedule to receive the selected volixibat dose (determined at the interim analysis) or placebo BID
- For the supplemental cohort, participants will be randomized with stratification (based on gestational age at randomization and presence/absence of gestational diabetes) after confirmation of study eligibility in a 1:1 ratio via a computer-generated randomization schedule to receive volixibat 20 mg BID or 80 mg BID.

Efficacy endpoints will be evaluated using stratification factors as covariates or stratification variables for analyses, as specified in [Section 6](#). If there is an imbalance in presumed prognostic baseline characteristics between treatment groups, efficacy evaluations may be performed that include these baseline values in efficacy analysis models as covariates; these evaluations will be considered sensitivity analyses.

For efficacy endpoints, the baseline value of the efficacy variable(s) will be included as a covariate in the efficacy analysis model.

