multiple imputation analysis for shift parameters 40, 41, ..., 50*/

%MIPARMS (DATA=XXXX, SMIN=40, SMAX=50, SINC=1, OUTPARMS=PARM2);
/*The following statements display the p-values that are associated with
the shift parameters.*/
PROC PRINT LABEL DATA=PARM2;
VAR SHIFT PROBT;
TITLE 'P-VALUES FOR SHIFT PARAMETERS';
LABEL PROBT='PR > |T|';
FORMAT PROBT 8.4;
RUN;
```

A sample of the SAS code for van Elteren test is provided as below:

```
proc nparlway data=adef ;  
  strata BLGSTAGE BLITCHRO BLGDIAB;  
  class trt01p;  
  var chg;  
run;
```

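### SAP 6.3 leaves two possible tests for change in biomarkers, and its general rule does not adjust for the biomarker's own baseline

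*SAP*

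**What the plan says.** **Protocol 10.4.1.4.** The change in total sBA from Week 3 to delivery is to be "tested using a randomization-based version of rank analysis of covariance". Change from baseline to delivery, and the ItchRO counterparts, are handled in the same way. For biomarkers: "The change in biomarkers will follow the same approach as other exploratory efficacy endpoints described above". No other between-arm test of a continuous change stands above that sentence. The covariate is not named there. Protocol 10.4.3.1 does name it, for the patient-reported outcomes: "rank ANCOVA with adjustment for baseline with the Mann-Whitney odds as the estimand".

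**SAP 6.3, opening rule for continuous endpoints.** "A p-value will be computed for between treatment comparisons using a van Elteren (vE) test". The SAP adds that "the van Elteren test, a stratified WMW test, can be used to adjust for the stratification factors". For the interval: "A non-strata adjusted 95% CI for the difference in means between treatment groups will also be presented", pooled or Satterthwaite depending on a test of equal variances.

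**SAP 6.3, later paragraphs.** The rank ANCOVA for sBA change to delivery is kept, with similar analyses for ItchRO. After the severity-scoring table, the protocol's biomarker sentence is repeated word for word.

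**SAP Appendix 3.** The van Elteren sample code analyses change from baseline with "strata BLGSTAGE BLITCHRO BLGDIAB". The variable names suggest gestational age, baseline ItchRO and gestational diabetes. None is a biomarker baseline.

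**SAP 3.3.** For efficacy endpoints, "the baseline value of the efficacy variable(s) will be included as a covariate in the efficacy analysis model".

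**SAP 1.** Deviations from the protocol are to be documented in Section 6 or 7. Section 6 records none on this point.

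**The concern.** In the protocol the biomarker cross-reference has one target. In the SAP the same words have two, because a van Elteren rule for all continuous exploratory endpoints now precedes the rank ANCOVA. The two methods differ in whether the biomarker's own baseline is used, so they can give different p-values from the same data, and the choice could be made after the results are known.

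The endpoints concerned are 7αC4, FGF-19, autotaxin, progesterone sulfate and GLP-1. Protocol 4.4 treats fasting 7αC4 as a measure of the degree of IBAT inhibition and relies on it for dose justification, so these data will be read as evidence on mechanism. Analysing raw change gives up precision that a baseline already collected would supply, and it leaves chance baseline imbalance in the estimate.

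**Working it through.** **1. Tracing the text.** Both documents send biomarker change to a method described earlier in the section.

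| Document | Continuous methods standing above the biomarker sentence |
|---|---|
| Protocol 10.4.1.4 | Rank ANCOVA only |
| SAP 6.3 | Van Elteren with a two-sample CI (general rule); rank ANCOVA (sBA and ItchRO change to delivery) |

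The sample code leans towards van Elteren. It runs on change, yet sBA and ItchRO change to delivery go to rank ANCOVA (SAP 6.3), as do the patient-reported outcomes (SAP 8), and the continuous perinatal outcomes have no baseline and so no change score. Biomarkers are the natural remaining use. That is inference from sample code, not a stated assignment.

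**2. The plan's own figure.** The documents give no sample size, SD, correlation or power for any biomarker. The only power statement is for the primary endpoint (Protocol 10.1: 100 per arm, 80% power, difference 10, SD 25, two-sided 0.05). It reproduces: 99 per arm are needed, and power at 100 per arm is 80.7% (normal) or 80.4% (t). It serves here only to fix the arm size.

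**3. Interval width.** Let s0 and s1 be the baseline and follow-up SDs and ρ their correlation.

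- Variance of raw change: s0² + s1² − 2ρ·s0·s1
- Baseline-adjusted variance: s1²(1 − ρ²)
- Difference: (s0 − ρ·s1)², never negative, and zero when ρ·s1 = s0

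With k = s1/s0, the CI width ratio (raw change over adjusted) is √[(1 + k² − 2ρk) / (k²(1 − ρ²))]. With equal SDs it reduces to √[2/(1 + ρ)]; at ρ = 0.3 that is √(2/1.3) = 1.24. At k = 2 and ρ = 0.9 it is √(1.4/0.76) = 1.36.

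| k (assumed) | ρ = 0.3 | ρ = 0.5 | ρ = 0.7 | ρ = 0.9 |
|---|---|---|---|---|
| 1 | 1.24 | 1.15 | 1.08 | 1.03 |
| 1.5 | 1.07 | 1.02 | 1.00 | 1.13 |
| 2 | 1.02 | 1.00 | 1.04 | 1.36 |

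If follow-up values were less variable than baseline, the loss would be larger: at k = 0.75 the ratios over the same correlations run from 1.34 to 1.47.

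**4. The rank tests themselves.** The formula above concerns means, so the two tests were also simulated: 100 per arm, eight strata unrelated to the biomarker, normal data, equal SDs, 2,000 runs, and an effect set to give 80% power for a parametric ANCOVA.

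| ρ | Van Elteren on change | Rank ANCOVA with baseline |
|---|---|---|
| 0.3 | 58% | 73% |
| 0.5 | 61% | 72% |
| 0.7 | 68% | 73% |
| 0.9 | 70% | 73% |

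With no effect, both tests rejected in about 4% to 6% of runs, so the issue is precision, not error control.

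**The case against.** Several stronger readings are tempting, and the documents do not support them.

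- *The SAP replaces rank ANCOVA with van Elteren for biomarkers.* It does not say so. Rank ANCOVA remains in SAP 6.3 for the other change endpoints and stands above the biomarker sentence, so it is a fair target.
- *The van Elteren test is unadjusted.* It is stratified. What it lacks is the biomarker's own baseline. Only the separate mean-difference CI is free of both strata and baseline.
- *The SAP widens the protocol's intervals.* Van Elteren yields a p-value and no interval, and protocol 10.4.1.4 plans no CI for biomarker change. The width comparison is between the SAP's CI and a baseline-adjusted one that could be reported instead.
- *The protocol prescribes baseline adjustment for biomarkers.* Section 10.4.1.4 names no covariate. Baseline is the natural reading of an analysis of covariance on change, and 10.4.3.1 says so for the patient-reported outcomes, but it remains a reading.

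The conflict with SAP 3.3 is also conditional: it disappears if the cross-reference means rank ANCOVA. The departure is judged against the current protocol, whereas SAP 1 says the SAP was written to Version 1. Finally, the size rests on assumed inputs. With follow-up SD twice baseline, the width excess at correlations 0.3 to 0.7 is only 0% to 4%.

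All of this stands, and it limits the point. It does not remove the ambiguity, or the fact that the SAP's stated default leaves out a baseline that is already measured.

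**Conclusion.** SAP 6.3 leaves the test for biomarker change open between two methods. If its general rule governs, the analysis departs from protocol 10.4.1.4 and SAP 3.3 without a recorded deviation, and the mean-difference CI is about 8% to 24% wider than a baseline-adjusted one (correlations 0.7 down to 0.3, equal SDs). Across correlations 0.3 to 0.9 and SD ratios of 1 to 2, the excess is 0% to 36%. All correlations and SD ratios are assumptions. Apart from one residual degree of freedom, the adjusted interval is never wider in expectation.

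A reader might infer that a study conclusion is at risk. It is not: the testing hierarchy (Protocol 10.4.1.2, SAP 3.5) covers only sBA, ItchRO and the composite perinatal outcome at the stated time points, and biomarkers are exploratory. This is a low-severity point worth settling because the correction costs almost nothing.

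**What to change.** In SAP 6.3, state that change in each biomarker is tested by the randomization-based rank ANCOVA already in the plan, with that biomarker's baseline as covariate, and name the strata. Replace the unadjusted mean-difference CI for these endpoints with a matching baseline-adjusted estimate and CI. The Mann-Whitney odds and the software named for the patient-reported outcomes are one route already in the plan.

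Keep van Elteren for continuous outcomes with no baseline measurement, such as gestational age at delivery and birth weight percentile. Reword the opening rule, the biomarker cross-reference and the Appendix 3 sample code to agree with this and with SAP 3.3. If van Elteren is preferred for biomarkers after all, say so and record the deviation in Section 6.

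The cost is one paragraph and a small edit to sample code. No new data are needed: Table 1 of the protocol already schedules biomarker samples at baseline, and a change score requires the baseline value anyway, so adjusting for it excludes nobody further.

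### Time from randomization to delivery gets an unadjusted confidence interval beside a test stratified coarsely on gestational age; one model with continuous gestational age at randomization would give a tighter, consistent result

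*SAP*

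**What the plan says.** SAP 6.3 opens with a general rule for continuous exploratory endpoints.

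- **Test:** "A p-value will be computed for between treatment comparisons using a van Elteren (vE) test". On the strata it says: "presence of stratum factors such as gestational age or ItchRO(Obs) Score, the van Elteren test, a stratified WMW test, can be used to adjust". The sample code in SAP Appendix 3 uses "strata BLGSTAGE BLITCHRO BLGDIAB". I read the first variable as the gestational-age category, most naturally the randomization split at 32 weeks, but the SAP does not define it.
- **Estimate:** "A non-strata adjusted 95% CI for the difference in means between treatment groups will also be presented". On the choice between a pooled and a Satterthwaite interval: "A test of equality of variances will be performed".

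Later in SAP 6.3, "Mean time from randomization to delivery" and "Mean gestational age at delivery" appear in one list of endpoints whose treatment differences will be tabulated.

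Three other places bear on the method.

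- Protocol 10.4.1.4 says the change in sBA from Week 3 to delivery "will be tested using a randomization-based version of rank analysis of covariance", and refers continuous perinatal endpoints back to the approach above. It lists no covariates.
- SAP 6.3 keeps that rank method for the sBA and ItchRO changes to delivery. It then says continuous perinatal endpoints follow the approach of the other exploratory endpoints, without saying which one.
- SAP 3.3 says in general that the stratification factors enter efficacy analyses, as covariates or strata, in the way Section 6 specifies.

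**The concern.** Participants in Part 2 may enter from 20 weeks 0 days to 36 weeks 0 days (Protocol 5.1). A woman who enters early will usually have a long time to delivery whatever her treatment. That spread is fixed before the first dose, and an unadjusted difference in means carries all of it as noise. Gestational age at randomization is already collected, and gestational age is already a continuous covariate in the primary model (SAP 6.1.2).

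The second difficulty is coherence. The p-value would come from a rank test with coarse strata, and the interval from a difference in means with none. The two can disagree for reasons unrelated to treatment. For binary exploratory endpoints the same section pairs a stratified test with a stratum-adjusted interval, so the mismatch is confined to the continuous endpoints.

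At stake are the precision and readability of the result on prolongation of pregnancy. No confirmatory claim is involved.

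**Working it through.** **The plan's own figure.** SAP 1.3 gives 100 per arm, difference 10, SD 25 and two-sided 0.05 for 80% power. The standardized difference is 10 / (25 × √(2/100)) = 2.83. Power is 0.807 by the normal approximation and 0.804 by the noncentral t, so the figure reproduces. It concerns sBA only. The documents state no SD, precision or power for time to delivery.

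**Set-up.** Let R be gestational age at randomization, D gestational age at delivery and T = D − R. Let sR and sD be their SDs, ρ their correlation and k = sR/sD. At the same sample size,

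- Var(T) = sD² + sR² − 2ρ·sD·sR
- residual variance of T given R = sD²(1 − ρ²)
- width ratio, unadjusted to adjusted = √[1 + (k − ρ)²/(1 − ρ²)]

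**Inputs.** All are assumptions: sR 1.5 to 3.5 weeks, sD 1.5 to 2.5 weeks, ρ 0 to 0.3. The nearest anchors are in Protocol 4.3.2.1: mean 33 weeks 4 days at diagnosis in a cited case-control study, and median 34.4 weeks at randomization in a cited placebo-controlled trial.

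| sR | sD | ρ | Width ratio |
|---|---|---|---|
| 1.5 | 2.5 | 0.3 | √(1 + 0.30²/0.91) = 1.05 |
| 1.5 | 2.5 | 0 | √(1 + 0.60²) = 1.17 |
| 2.0 | 2.0 | 0 | √2 = 1.41 |
| 2.5 | 2.0 | 0 | √(1 + 1.25²) = 1.60 |
| 3.0 | 2.0 | 0 | √(1 + 1.50²) = 1.80 |
| 3.5 | 1.5 | 0 | √(1 + 2.33²) = 2.54 |

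The range is about 1.05 to 2.5. With sR 2.5 and sD 2.0 at 100 per arm, the 95% half-width is 1.972 × √(2/100) × √(2.5² + 2.0²) = 0.89 weeks unadjusted, and 1.972 × √(2/100) × 2.0 = 0.56 weeks adjusted.

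**Bounded entry.** Simulations kept R within 20 to 36 weeks and put delivery at least one week after entry. With median entry at 33.8 to 34.3 weeks, near the protocol's anchors, the ratio was 1.36 to 1.80. With median entry at 31.3 to 32.9 weeks it was 1.91 to 2.84.

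**How far the 32-week split goes.** In the same runs the unadjusted interval was 1.17 to 1.51 times as wide as one adjusted for the split. The split-adjusted interval was still 1.17 to 1.88 times as wide as one using continuous R.

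**The companion endpoint.** Because T = D − R, regressing T or D on treatment and R gives the same residuals, the same treatment coefficient and the same SE; only the coefficient on R changes, by 1. The unadjusted comparison of D has SE larger by only 1/√(1 − ρ²), which is 1.05 at ρ = 0.3. With sD 1.5 and 100 per arm, its SE is 1.5 × √(2/100) = 0.212 weeks. The adjusted SE is 0.211 at ρ = 0.1 and 0.202 at ρ = 0.3.

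**The variance pretest.** With n per arm, the pooled SE is √[((s₁² + s₂²)/2)(2/n)] and the unequal-variance SE is √[(s₁² + s₂²)/n]. These are the same number; only the degrees of freedom differ.

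**The case against.** The strongest reply is that little information is lost. Mean gestational age at delivery is in the same list, and its planned unadjusted comparison estimates the same treatment effect almost as precisely as the adjusted analysis of time to delivery. That stands, and it limits the consequence. It also supports the change: as planned, two listed endpoints that differ only by a pre-randomization quantity may show different estimates and intervals, whereas the adjusted linear model makes them agree.

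It can also be said that the unadjusted interval is valid under randomization and that the endpoint lies outside the three-step hierarchy in SAP 3.5. Both are right.

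Four stronger readings are tempting, and the documents do not support them.

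- **The comparison ignores gestational age.** Only the interval does. The test names it as a stratum factor.
- **Gestational age at entry drives most of the variance.** An eligibility range does not give a variance. At ρ = 0, entry explains more than half only if sR exceeds sD, and Protocol 4.3.2.1 expects participants to cluster towards the upper end of eligible gestational ages.
- **A narrow ratio such as 1.5 to 1.9 can be stated as fact.** At ρ = 0 that needs sR/sD between 1.12 and 1.62. With entry SD 1.5 to 2.0, delivery SD 2 and correlation 0.1 to 0.3, the ratio is only 1.11 to 1.35.
- **The SAP abandons the protocol's rank ANCOVA.** SAP 6.3 keeps it for sBA and ItchRO and is ambiguous for perinatal endpoints. The protocol names no covariates, so it never promised adjustment for gestational age here.

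**Conclusion.** The point holds in limited form. Under the general rule in SAP 6.3, the interval for time from randomization to delivery is unadjusted while its test is stratified coarsely, so estimate and p-value rest on different adjustments. The interval is valid but inefficient, at about 1.05 to 2.5 times the width of one adjusted for continuous gestational age at randomization. That range depends wholly on assumed SDs and correlation, and near its lower end the gain is small. The benefit is a tighter and internally consistent result for one exploratory endpoint; neither the primary analysis nor the testing hierarchy is affected. The change is worth making because it costs almost nothing. The variance pretest is a minor matter with equal arms.

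**What to change.** In SAP 6.3, specify for time from randomization to delivery one ANCOVA with treatment, continuous gestational age at randomization and the allocation factors in SAP 3.3 (gestational diabetes and highest sBA category; gestational age is already in as a continuous term). Take the treatment difference in weeks, its 95% interval and the p-value from that model. If the sponsor prefers the protocol's randomization-based rank ANCOVA, list the same covariates. A rank analysis does not itself give a difference in weeks, and the identity with gestational age at delivery holds only in the linear model.

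Reconcile Protocol 10.4.1.4 with SAP 3.3 and 6.3 on which method governs continuous perinatal endpoints. If the van Elteren test stays for others, define its strata: the sample code appears to use an ItchRO category, which is not an allocation factor, and has no term that looks like the sBA category, which is one.

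Optionally, replace the variance pretest with unequal-variance or robust standard errors throughout.

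The cost is SAP text and programming. No new data or participants are needed. The change should be fixed before Part 2 is unblinded.
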